12. ADMINISTRATIVE ASPECTS, MONITORING AND PUBLICATION	31
12.1Handling and storage of data and documents	31

12.2	Monitoring and Quality Assurance.....	31
12.3	Amendments.....	32
12.4	Annual progress report.....	32
12.5	Temporary halt and (prematurely) end of study report.....	32
12.6	Public disclosure and publication policy	32
13.	STRUCTURED RISK ANALYSIS.....	33
14.	REFERENCES	34

LIST OF ABBREVIATIONS AND RELEVANT DEFINITIONS

AE	Adverse Event
CCMO	Central Committee on Research Involving Human Subjects; in Dutch: Centrale Commissie Mensgebonden Onderzoek
COD	Check-up on demand
EPD	Electronic patient record system
FU	Follow-up
GCP	Good Clinical Practice
GDPR	General Data Protection Regulation; in Dutch: Algemene Verordening Gegevensbescherming (AVG)
HCP	Health care professional
IC	Informed Consent
LROI	Dutch Arthroplasty Register
METC	Medical research ethics committee (MREC); in Dutch: medisch-ethische toetsingscommissie (METC)
Review committee	Medical research ethics committee (MREC) or CCMO
RFU	Routine follow-up
(S)AE	(Serious) Adverse Event
Sponsor	The sponsor is the party that commissions the organisation or performance of the research, for example a pharmaceutical company, academic hospital, scientific organisation or investigator. A party that provides funding for a study but does not commission it is not regarded as the sponsor, but referred to as a subsidising party.
THA	Total hip arthroplasty
TKA	Total knee arthroplasty
UAVG	Dutch Act on Implementation of the General Data Protection Regulation; in Dutch: Uitvoeringswet AVG
WMO	Medical Research Involving Human Subjects Act; in Dutch: Wet Medisch-wetenschappelijk Onderzoek met Mensen

SUMMARY

Rationale: Clinical guidelines recommend routine follow-up (RFU) consisting of an X-ray and a clinical visit within 3 months and at 1 year after total hip arthroplasty (THA) and knee arthroplasty (TKA). RFU after 5 years (THA) or every 5 years (TKA) might also be worth considering. As revisions are rare and seldom without symptoms, the added value of RFU can be questioned. Consequently, this already leads to variability in clinical practice, as some hospitals already conduct check-ups only upon the request of the orthopaedic surgeon or patient (COD). However, replacing RFU by only COD might not be without risks. A recent NIHR report (2022) recommends that no further RFU is required before 10 years in patients with well-studied implants not at high risk of developing problems. However, they do not give evidence for or insight in the cost-effectiveness of RFU at 10 years and recommend to further research the additional value of RFU after 10 years. We expect that replacing RFU at 10 years by COD will be (cost-)effective without compromising outcomes relevant to patients.

Objective: Primary: investigate the (cost-)effectiveness of replacing RFU after THA and TKA at 10 years by COD by comparing the complications and clinical visits between patients with COD versus RFU at 10 years after THA and TKA. Secondary: investigate the effect of COD compared to RFU at 10 years after THA and TKA on surgical interventions, physical function, quality of life, pain and costs. Investigate the effect of informing patients about COD on complications, clinical visits, surgical interventions, and costs.

Study design: Randomized controlled trial with 3 arms

Study population: Patients who had a primary THA or TKA 10 years ago because of osteoarthritis, were 50 years or older at the time of THA or TKA, are still alive and had no revision arthroplasty, bilateral surgery or are already participating in the study due to another hip or knee surgery. Patients will be identified using the Dutch Arthroplasty Register (LROI) and the electronic patient record system (EPD). In total 1,500 patients will be included.

Intervention: COD (intervention): no follow-up visit 10 years after THA or TKA but only check-ups requested by both the health care professional (HCP) or the patient. The intervention group will be split into two groups: one group will be informed about the study and will fill out questionnaires (active COD), one group will not be contacted to avoid any trigger to contact a HCP (passive COD). RFU (control): follow-up visit 10 years after THA or TKA combined with questionnaires.

Main study parameters/endpoints: primary outcomes: complications (clinical outcome), healthcare consumption (process outcome); secondary outcomes: PROMIS physical function, surgical interventions, NRS pain, NRS satisfaction, EQ-5D-5L, and costs for healthcare and societal perspectives.

Nature and extent of the burden and risks associated with participation, benefit and group relatedness: No additional risks are expected compared to standard care, as both RFU and COD 10 years after THA or TKA are part of current clinical practice. Patients are required to spend time completing questionnaires. Only the RFU group will be asked to visit the hospital.

1. INTRODUCTION AND RATIONALE

Clinical Dutch guidelines recommend routine follow-up (RFU) consisting of an X-ray and clinical visit within 3 months and at 1 year after total hip arthroplasty (THA) and total knee arthroplasty (TKA) [1, 2]. RFU after 5 years (THA) or every 5 years (TKA) might also be worth considering. However, the added value of RFU can be questioned, as registry data show excellent survival after THA and TKA [3] and revisions are rare and seldom without symptoms [4-7]. Currently, clinical practice demonstrates significant variation in RFU, as some hospitals have already decided to discontinue RFU and instead perform check-ups only upon the request (COD) of the patient or orthopedic surgeon. This practice variation was confirmed by a national survey performed in 2019 among orthopaedic surgeons (non-published results). So, both RFU and COD are currently used in clinical practice, which is also acknowledged by the Dutch Orthopaedic Society (NOV).

There is equipoise among orthopaedic surgeons; a widely shared feeling of genuinely not knowing what the best course of action is. What is the risk of missing a complication? Do patients report issues promptly? For example, osteolysis (break down of bone tissue) and wear of the prosthesis can occur without symptoms. When discovered early, this can be monitored and managed by a relatively simple revision surgery. However, when discovered late, this can result in catastrophic failure (i.e. unexpected and unannounced failing of the prostheses with large consequences) and therefore a more complex revision surgery, with higher costs and more risks for the patient. There is willingness to adjust clinical practice, but also hesitation due to the risks of providing suboptimal care and missing a complication at the long term. In other words, replacing RFU with only COD might not be without risks, i.e. missed complications, reduced patient satisfaction or physical function.

Current guideline recommendations are of low level evidence. Both guidelines suggest that the added value of RFU is likely limited, but convincing research is lacking [1, 2].

Furthermore, previous studies did not give evidence for mid- and long-term RFU and did not report the effect on a combination of (potentially missed) complications, costs, and PROMs such as physical function. Most studies retrospectively evaluated complications, revisions, radiographic abnormalities or change in management, and were underpowered [6, 8-12]. Current RCTs only compared a web-based follow-up (FU) to routine X-rays and a clinical visit, but did not eliminate FU [13, 14].

Little information is available on the effectiveness of long-term (>10 years) RFU [15, 16]. A retrospective medical chart review showed that of 501 patients with RFU, 84% had either no symptoms or a musculoskeletal concern unrelated to the prosthesis [7]. Without symptoms, a

change in clinical management was 7x less likely and the risk of revision was 10x lower than with symptoms. When combining the reported percentages of asymptomatic patients who undergo revision surgery (0.6-3.6%, [6, 7]) with the 12 year LROI survival data, COD may negatively affect 0.03-0.2% of the population of interest. On the other hand, RFU may negatively affect patients due to overdiagnosis and overtreatment.

A recent NIHR report (2022) recommends that no further RFU is required before 10 years in patients with well-studied implants not at high risk of developing problems [17]. These recommendations are mainly based on expert opinions and retrospective data. However, this report does not give evidence for or insight in the cost-effectiveness of RFU at 10 years and they recommend to further research the additional value of RFU after 10 years. In this study, we will address this knowledge gap by providing high level evidence. We expect that RFU at 10 years can be safely replaced by COD after THA and TKA and that it will be (cost-)effective without compromising outcomes relevant to patients.

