4. STUDY POPULATION

4.1 Population (base)

Patients will be identified using the LROI register and the EPD. In 2015, 28,872 THA and 24,244 TKA were performed in the Netherlands [3]. The participating centres indicated that they performed between 400 and 800 THA and TKA per year. Taking into account a mortality rate of 16% 10 years after THA or TKA [18, 19], a revision rate of 6% 10 years after THA and TKA [3] and that 33% of the patients might not want to participate, the patient population will still be large enough to obtain our required sample size.

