4.4 Sample size calculation

We carefully determined the required number of patients to ensure reliable outcome estimates in collaboration with co-creating stakeholders and by consulting orthopaedic surgeons using an online survey on what constitutes convincing evidence. The agreed sample size is 250 patients per group. Therefore, we plan to randomize 250 patients per study group resulting in a total of 750 THA and 750 TKA patients.

To provide a rough indication of the statistical power, we used the online power calculator tool available on Sealed Envelope [20]. The sample size calculation is based on the comparison of RFU vs. active COD as the primary analysis. For this calculation, we assumed that the actual complication rate in both groups is 10%. With the agreed number, it is possible to detect a clinical relevant difference of 10% in complications between the two groups. If there is truly no difference between active COD and RFU, 190 patients per group are needed to be 80% sure that the limits of a two-sided 95% confidence interval will exclude a difference between active COD and RFU of more than 10%. Anticipating 20-25% loss to follow up, we plan to randomize 250 patients.

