10. STATISTICAL ANALYSIS

All analyses will be performed separately for THA and TKA and will be performed using IBM SPSS statistics (SPSS software version 28.0) or R. Categorical data will be presented as numbers and percentages. Continuous variables will be presented by mean and standard deviation in case of a normal distribution. In case of non-normality, median and interquartile range will be given.

Mixed models are used to deal with missing data; when necessary and possible we will perform multiple imputation.

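### Rare surgical outcomes are modelled separately for THA and TKA at about 1-2 revisions per arm, and the protocol does not say that its anticipated harm of 0.03-0.2% lies beyond the trial's reach

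*Protocol*

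**What the plan says.** - **Anticipated harm.** Protocol section 1 combines the "reported percentages of asymptomatic patients who undergo revision surgery (0.6-3.6%, [6, 7]) with the 12 year LROI survival data" and concludes that "COD may negatively affect 0.03-0.2% of the population of interest". The same section gives the investigators' expectation: "We expect that RFU at 10 years can be safely replaced by COD after THA and TKA".
- **Size.** Section 4.4 plans 250 patients per group within each procedure (750 THA and 750 TKA). It assumes a 10% complication rate in both groups and says that "it is possible to detect a clinical relevant difference of 10% in complications between the two groups". The basis is that "190 patients per group are needed to be 80% sure that the limits of a two-sided 95% confidence interval will exclude a difference" of more than 10 points, raised to 250 for 20-25% loss.
- **Split by procedure.** Section 10: "All analyses will be performed separately for THA and TKA". No exception is given for rare outcomes.
- **Models for surgery.** Section 10.2 compares the number of surgical interventions across the three groups with a Poisson mixed model, and their type with a logistic mixed model. Both have a random intercept for centre and adjustment for confounders. The Poisson sentence names complications, but it stands in the paragraph on surgical interventions and I read it that way.
- **Background rate.** Section 4.1 cites "a revision rate of 6% 10 years after THA and TKA".
- **Follow-up and sites.** Section 3: one year, ten hospitals.

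**The concern.** The harm that section 1 fears is silent osteolysis or wear found late and ending in a more complex revision. Surgical intervention is the collected outcome closest to it, though an imperfect one. Within one procedure so few such events are expected that a mixed model with a centre effect and covariates may fail to converge, or may return an interval too wide to use. The rule in section 10 closes off the simplest gain in precision, which is to combine the two procedures.

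The protocol also never sets its own harm estimate against what the design can show. A finding of no difference in complications or surgery is likely whether or not harm of 0.03-0.2% exists. Section 3 reports that the orthopaedic association has committed to implementing the results, so a null result read as evidence of safety could change practice on a question that the trial did not answer.

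**Working it through.** **1. The plan's sample size.** Equivalence on a risk difference, 10% in both groups, margin 10 points, 2.5% per side, 80% power:

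n = [2 × 0.1 × 0.9] × (1.960 + 1.282)² / 0.10² = 189.1, rounded up to 190.

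The stated 190 reproduces. With 250 randomised and 20-25% loss, 188 to 200 remain. The arithmetic is sound for all complications.

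**2. The plan's harm figure.** Asymptomatic share × revision rate. With the 6% of section 4.1: 0.6% × 6% = 0.036% and 3.6% × 6% = 0.216%. The 12-year survival value is not printed; an assumed 5% gives 0.6% × 5% = 0.03%. The range of 0.03-0.2% is therefore consistent with the protocol's other figures.

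**3. Affected patients in one active COD arm of one procedure.** Expected number = n × r; chance of none = (1 − r)^n.

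| n | r | expected | chance of none |
|---|---|---|---|
| 250 | 0.03% | 0.08 | 93% |
| 250 | 0.2% | 0.50 | 61% |
| 190 | 0.03% | 0.06 | 94% |
| 190 | 0.2% | 0.38 | 68% |

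For scale, detecting 0% against 0.2% directly would take about 3,920 patients per arm.

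**4. Events available to the models in section 10.2.** Assumption: the 6% over ten years is spread evenly, so 0.6% per year. The year after the ten-year point may differ, so 0.2% and 1% are also shown.

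- Per arm and procedure at 0.6%: 250 × 0.006 = 1.5; 190 × 0.006 = 1.1. At 0.2% and 1% with n = 250: 0.5 and 2.5.
- Over all three arms of one procedure: 750 × 0.006 = 4.5 events across ten hospitals. Most hospitals would have one or none.
- Chance that one arm has no event: 0.994^250 = 0.22. Chance that RFU or active COD (or both) has none, so that an ordinary rate or odds ratio between them has no finite estimate: 1 − (1 − 0.22)² = 39%. At 0.2% and 1% per year it is 84% and 16%. Pooled over procedures (500 per arm) at 0.6% it falls to 10%.

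**5. Precision of the risk difference, RFU versus active COD.** Half-width = 1.96 × √[2r(1 − r)/n]:

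| Annual rate r | n = 250 (one procedure) | n = 500 (pooled) |
|---|---|---|
| 0.2% | 0.78 points | 0.55 points |
| 0.6% | 1.35 points | 0.96 points |
| 1% | 1.74 points | 1.23 points |

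These ignore losses. With 190 and 380 per arm at 0.6% the half-widths are 1.55 and 1.10 points. The normal approximation is rough at such counts and shows scale only. Pooling narrows the interval by a factor of √2, about 29%. Even the narrowest pooled value, 0.55 points, exceeds the upper harm figure of 0.2 points.

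**The case against.** **The protocol does not claim to prove safety.** This stands. Safe replacement appears once in the introduction, as an expectation. The primary objective in section 2 is (cost-)effectiveness through complications and visits. Section 4.4 calls its power figure a rough indication and says what difference 190 per group can exclude. Only the limit regarding 0.03-0.2% is unstated.

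**A pooled supplementary analysis belongs in a statistical analysis plan.** Ordinarily yes, and none is at hand. But section 10 fixes all analyses as separate, so a plan that pooled would depart from the protocol. The exception therefore belongs in section 10.

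**Stronger readings that the document does not support:**

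- A reader might infer that the margin is wrong because 10 points is 50 times 0.2% and 333 times 0.03%. The two figures measure different things. The margin concerns all complications at an assumed 10% rate, including complaints or X-ray changes that lead to extra follow-up (section 8.1.1). The harm figure concerns missed asymptomatic revisions. The ratio says nothing about whether the margin suits its own endpoint.
- A reader might pool all 1,000 COD patients and quote an upper limit of 0.37%. That limit requires zero events. At 0.6% per year about 6 are expected, the chance of none is 0.994^1000 = 0.2%, and the exact upper limit for 6 in 1,000 is 1.30%. It would also mix active COD patients, who consented, with passive COD patients, who were never approached.
- A reader might take one-year surgery counts as a measure of missed failures. By the reasoning in section 1, RFU may itself lead to early surgery that COD delays, so missed cases could appear as fewer operations under COD.

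**Conclusion.** The concern holds in a limited form. Sample size and margin reproduce and are not in question. Two things need correcting.

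First, applying mixed models with a centre intercept to surgical interventions, separately by procedure, rests on about 1-2 revisions per arm. A pooled, procedure-stratified risk difference would bring the half-width from about 1.35 to 0.96 points using data already collected. This depends on spreading the 6% evenly over ten years; across 0.2-1% per year the gain is 0.78 to 0.55 points and 1.74 to 1.23 points. Surgical interventions also include procedures other than full revision, so their count may be higher than the revision rate suggests.

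Second, the protocol should say that harm of 0.03-0.2% can be neither confirmed nor excluded, with or without pooling. The trial can still inform visits, X-rays, costs and patient-reported outcomes, and can exclude a large excess of complications. It does not support a conclusion of safe replacement from a null result on complications or surgery. This is a worthwhile, inexpensive improvement, not a fatal flaw.

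**What to change.** **Section 10.** Keep the separate THA and TKA analyses. Add a prespecified exception for rare outcomes (any surgical intervention; revision): RFU versus active COD pooled over THA and TKA, stratified by procedure, reporting the risk difference with an exact or score 95% CI (for example a stratified Miettinen–Nurminen interval). Show the counts by arm and procedure beside it.

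**Section 4.4.** State that the design addresses only differences of about 10 points in all complications; that it cannot confirm or exclude the harm of 0.03-0.2% estimated in section 1; and that one-year surgery counts do not measure missed silent failures, so a null result will not be read as showing safe replacement.

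**Cost.** Protocol wording and one additional analysis, with no extra patients or data collection. The pooled estimate assumes similar effects in THA and TKA, which these data can hardly test, and the stated reach of the trial becomes less favourable.

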2. OBJECTIVES

Primary Objective: Investigate the (cost-)effectiveness of replacing RFU after THA and TKA at 10 years by COD by comparing complications and clinical visits between patients with COD versus RFU at 10 years after THA and TKA, after a follow-up of 1 year.

Secondary Objective(s): Investigate the effect of COD compared to RFU at 10 years after THA and TKA on surgical interventions, physical function, quality of life, pain and costs , after a follow-up of 1 year.

Investigate the effect of informing patients about COD on complications, clinical visits, surgical interventions, and costs.

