3. STUDY DESIGN

During the grant application process, all relevant stakeholders were involved in setting up this study protocol during a co-creation process. The co-creation team consisted of representatives from patient associations, healthcare insurers, the knowledge institute of the federation of medical specialists, the national healthcare institute, methodological and statistical expertise, the Netherlands Orthopaedic Association (NOV), the ZE&GG program for appropriate healthcare, and the project team. ZE&GG organized meetings to discuss crucial points with the stakeholders, which resulted in a well-considered research protocol approved by all involved stakeholders. The NOV signed a declaration of support and commits to implementation of the results.

In this study a randomized controlled trial with 3 arms will be performed. Patients will be randomized 1:1:1 in the following groups:

[figure not shown]
1. RFU: routine follow-up at 10 years after THA or TKA (control)
2. Active COD: No RFU at 10 years. Patients will be informed about the study and complete questionnaires. Check-ups are scheduled only on demand by the patient or health care professional (HCP) (intervention)
3. Passive COD: No RFU at 10 years. Patients will not be informed about the study to avoid any trigger to contact a HCP and will not complete questionnaires (intervention)

Patients will be followed for 1 year after RFU or COD (11 years after surgery). Informing the patients about the study and letting them complete questionnaires might result in trigger bias to contact a HCP. Therefore, patients in the intervention group will be divided into two groups: 1) one group will be informed about the study and complete questionnaires (active COD), 2) the other group will not be contacted and informed about the study to avoid trigger bias (passive COD). Of the latest group, only data from the LROI and EPD will be used. The control group will receive RFU at 10 years after THA or TKA and will complete questionnaires. Both groups completing questionnaires (active COD and RFU group) will be actively asked to participate in the study and to complete questionnaires and therefore will be randomized after informed consent.

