8.3 Study procedures

This study will be conducted in 10 Dutch hospitals across the Netherlands. Patients will be recruited using the LROI register and EPD. After inclusion, baseline characteristics will be obtained from the EPD and LROI register. Information on patient background will be collected to explore potential differences in follow-up needs, including among patients with different ethnic backgrounds. Previous research shows that people with a migrant background visit specialists and hospitals less often than native Dutch patients with similar health and SES [21]. Acknowledging the sensitivity of this topic, a 'prefer not to say' option is provided.

Patients will be scheduled for a clinical visit or not depending on the randomization group. The clinical visit contains of a check by the orthopaedic surgeon or orthopaedic resident and an X-ray. Additionally, a physical examination can be performed in case of concerns.

Information about the clinical visit will be collected. The patient or the HCP can also schedule a clinical visit in case of concerns, pain or symptoms. Information about these visits will also be collected.

Patients randomized to the active COD or RFU group will be asked to complete the questionnaires online or on paper. Completion time will be around 10-25 minutes. Table 1 depicts the data collection and assessments at baseline and during follow-up appointments.

Study data will be collected onto an electronic case report form (eCRF) in Castor EDC. The primary outcome will be measured at 11 years after surgery, i.e. 1 year after RFU or COD at 10 years. EQ-5D-5L and costs will be measured at 10 years after surgery (baseline), and at 3, 6, and 12 months after baseline in the RFU and active COD group. The other outcomes will be measured only at 10 years (baseline) and 11 years after surgery (end point).

Table 1: Overview of data collection and assessments.

	Baseline (10 years after surgery) (+/- 30 days)	In case of check-up on demand (10-11 years after surgery)	3 months (+/- 30 days)	6 months (+/- 30 days)	12 months (11 years after surgery) (+/- 30 days)
Clinical visit	X*	X			
Physical examination [#]	X	X			
X-ray	X*	X [#]			
Healthcare consumption	X	X	X	X	X
Questionnaires:**					
PROMIS	X				X
EQ-5D-5L	X		X	X	X
NPRS	X				X
NSRS	X				X
Costs	X		X	X	X

* Only RFU group

[#] In case of concerns

** Not for passive COD group

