11.2 Recruitment and consent

First, each participating center will select patients who had a THA or TKA 10 years ago using the LROI register and EPD. From this list, all patients will be selected who meet the inclusion and exclusion criteria. From the remaining list, patients will be randomized in a 1:2 ratio into a passive and active group. Patients in the active group will be approached for participation.

The initial contact regarding the study will be made by a physician working in the orthopaedic department of the hospital where the surgery was performed, by asking permission if he/she can be approached for the study. A researcher or research coordinator will contact the patient by phone, or at the outpatient department to assess their suitability for participation based on their medical history and the study's inclusion and exclusion criteria. The researcher will provide a brief overview of the study's purpose and procedures and offer the opportunity for patients to ask any initial questions about the study. If the patient expresses interest in the study, the patient information letter including the informed consent form will be sent by mail, along with a return envelope, and/or e-mail ensuring the patient has adequate time to review the study details. The patient will be contacted after at least 5 days by the research team. The researcher will discuss the patient information letter and the patient has the opportunity to ask further questions. Once the patient agrees to participate, they will sign the consent form and return it to the research team. The researcher will sign and return a copy of the fully signed consent form to the patient, ensuring that both the investigator and the patient have a complete signed informed consent.

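### Active versus passive COD compares study contact with no contact, so it cannot answer the secondary objective on the effect of informing patients about COD

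*Protocol*

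**What the plan says.** The objective in section 2 of the protocol, also given in the Summary, is: "Investigate the effect of informing patients about COD on complications, clinical visits, surgical interventions, and costs". It names one factor.

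Section 3 defines the two arms that bear on it. For active COD: "Patients will be informed about the study and complete questionnaires". For passive COD: "Patients will not be informed about the study to avoid any trigger to contact a HCP and will not complete questionnaires (intervention". The same section gives the reason for splitting the intervention group: "Informing the patients about the study and letting them complete questionnaires might result in trigger bias to contact a HCP". It also says that patients in the RFU and active COD groups are actively asked to take part and "therefore will be randomized after informed consent".

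Section 11.2 describes the approach to the active group. A physician first asks permission for the approach. Next, "A researcher or research coordinator will contact the patient by phone, or at the outpatient department". An information letter follows, then a further contact after at least five days, then consent. Section 8.3 and Table 1 set the questionnaire schedule. Sections 8.1.2 and 8.2 confine passive COD to data from the EPD and the LROI. Section 10.2 repeats the primary models with all three groups.

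**The concern.** The objective attributes the contrast to informing patients about COD, whereas section 3 attributes a possible extra inclination to seek care to study information and questionnaires jointly. If active COD shows more visits or more recorded complications than passive COD, the objective as worded invites the reading that informing patients caused it. Questionnaires, recruitment contacts or the kind of patient who consents could produce the same result.

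The question has practical weight. Section 5 notes that where hospitals stopped RFU, many patients were not told individually, and section 3 records that the orthopaedic association has committed itself to implementing the results. A hospital moving to COD would want to know whether to tell its patients. This trial cannot say, although its objective suggests that it will.

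**Working it through.** **1. The plan's own figure.** Section 4.4 gives 190 evaluable patients per group for RFU versus active COD. It reproduces as an equivalence calculation with 10% complications in both groups, a 10-point margin, a two-sided 95% interval and 80% power split over the two limits:

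n = 2 × 0.10 × 0.90 × (1.960 + 1.282)² / 0.10² ≈ 189.1, rounded up to 190.

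The figure is not in dispute. It concerns a different comparison, and the protocol gives none for active versus passive COD.

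**2. What differs between the two COD arms.**

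| Component | Active COD | Passive COD | Source |
|---|---|---|---|
| Told about the study | yes | no | section 3 |
| Recruitment contacts | yes | no | section 11.2 |
| Informed consent | yes | no | sections 3, 8.2 |
| EQ-5D-5L | 0, 3, 6, 12 months | none | section 8.3, Table 1 |
| Cost questionnaire | 0, 3, 6, 12 months | none | section 8.3, Table 1 |
| PROMIS, NPRS, NSRS | 0, 12 months | none | section 8.3, Table 1 |

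Scheduled instrument completions in active COD: 2 instruments × 4 rounds + 3 instruments × 2 rounds = 14, against 0 in passive COD. Of these, 14 − 5 = 9 fall at 0, 3 or 6 months, early enough to prompt a visit within the outcome year. According to section 8.3, EQ-5D-5L asks about mobility and pain or discomfort, so symptoms are raised at 3 and 6 months too.

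**3. Identifiability.** Write the expected active minus passive difference as

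D = I + C + Q + S,

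where I is the effect of information, C of recruitment and consent contact, Q of questionnaires (interactions absorbed), and S is the difference in who is in the arm. The trial supplies one estimate, D, for four unknowns. No arm is informed without being consented and sent questionnaires, and the three-group model in section 10.2 has only a group effect. A larger sample makes D more precise but does not separate I from the rest. In addition, the information is described as being about the study. No stand-alone message about COD is described.

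**4. The selection term S.** Under section 8.2 the passive group is split off before any contact, and active COD is allocated after consent. Passive COD therefore includes people who would have declined. Section 4.1 allows for 33% not wanting to participate. Assume 10% complications in consenters (the rate in section 4.4), a rate p in would-be decliners (not given in the protocol, so varied), and no effect of information, contact or questionnaires. Then

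S = 0.10 − (0.67 × 0.10 + 0.33 × p) = 0.33 × (0.10 − p).

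| p (assumed) | Passive COD rate | Active minus passive |
|---|---|---|
| 5% | 8.35% | +1.65 points |
| 10% | 10.00% | 0 |
| 15% | 11.65% | −1.65 points |
| 20% | 13.30% | −3.30 points |

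**5. Costs.** Costs outside the hospital come from questionnaires (sections 8.1.2 and 8.3), which passive COD does not receive. For this objective, costs can be compared only as far as the EPD and LROI record them.

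**The case against.** The strongest defence is that the wording is shorthand. Section 3 defines the arms by information and questionnaires together and says openly why the passive arm exists. Read with that section, the objective means active versus passive COD and no more. This is fair as to intent, and the design can serve as a check on the influence of study contact. But the objective as written names one factor, and no later analysis plan can separate components that never occur apart.

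Several stronger readings are tempting, and the documents do not support them:

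- *That pain and function are asked about in full at all four rounds.* Table 1 places PROMIS, NPRS and NSRS only at baseline and 12 months. At 3 and 6 months the prompting comes from EQ-5D-5L and the cost questionnaire.
- *That each round takes 10 to 25 minutes.* Section 8.3 says "Completion time will be around 10-25 minutes" without tying the range to each round, and the rounds differ in content.
- *That the protocol already draws a care-policy conclusion about informing patients.* It does not. The objective only says that the effect will be investigated, and the budget-impact scenarios in section 10.2.1 do not compare informed with uninformed COD.
- *That the contrast, once renamed, gives a clean estimate of trigger bias.* The selection term in the working rules this out.

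**Conclusion.** The point stands as a mismatch between the objective (section 2 and the Summary) and the arms (section 3). Active versus passive COD estimates the combined effect of study information, recruitment and consent contact, and questionnaires, together with a difference in who is included. It does not estimate the effect of informing patients about COD. That conclusion follows from the arm definitions and needs no numerical assumption.

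The size of the misattribution cannot be derived from the protocol. The range of +1.65 to −3.3 percentage points illustrates the selection component alone. It rests on 33% non-participation, 10% complications in consenters and assumed rates of 5% to 20% in decliners.

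The consequence is limited to one secondary objective. A reader might infer that the main result is compromised as well. It is not: RFU and active COD are both randomised after consent and both complete questionnaires, so neither consent selection nor the presence of study contact separates those two arms.

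**What to change.** In section 2 and the Summary, reword the objective as the comparison of COD with study contact (information, consent and questionnaires) versus COD without study contact, on complications, clinical visits, surgical interventions and costs obtainable from the EPD and LROI.

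Add two statements:

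1. A difference between the arms cannot be attributed to informing patients alone.
2. The contrast is not a pure estimate of trigger bias, because active COD includes only consenters while passive COD also includes people who would have declined.

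The cost is a change of wording and a narrower secondary claim. Arms, data collection, sample size and the primary analysis stay as they are.
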